3. PARTICIPANT SELECTION AND ENROLLMENT PROCEDURES

3.1 Inclusion Criteria

- Patients must be at least 18 years of age;
- Patients must be able to provide informed consent;
- Histologically proven low-grade or intermediate-grade PC;
- Scheduled to undergo targeted local therapy (HDR brachytherapy).

3.2 Exclusion Criteria

- Inability to lie still for the entire imaging time;
- Inability to complete the needed investigational and standard-of-care imaging examinations due to other reasons (severe claustrophobia, radiation phobia, etc.);
- Any additional medical condition, serious intercurrent illness, or other extenuating circumstance that, in the opinion of the Investigator, may significantly interfere with study compliance;
- Metallic implants (contraindicated for MRI).

3.3 Informed Consent Process

All participants will be provided a consent form describing the study with sufficient information for participants to make an informed decision regarding their participation. Participants must sign the IRB-approved informed consent prior to participation in any study specific procedure. The participant must receive a copy of the signed and dated consent document. The original signed copy of the consent document must be retained in the medical record or research file.

3.4 Study Timeline

3.4.1 Primary Completion:

The study will reach primary completion 24 months from the time the last subject completes the first scan.

3.4.2 Study Completion:

The study will reach study completion 84 months from the time the study opens to accrual.

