1. OBJECTIVE

Specific Aims

Aim 1: ^{68}Ga -RM2 PET/MRI and ^{68}Ga PSMA-11 PET/MRI detection of PC. We will investigate the performance of the new GRPr-binding PET radiopharmaceutical, ^{68}Ga -RM2, and compare it to the currently most widely investigated (but not FDA-approved) PC PET radiopharmaceutical, ^{68}Ga PSMA-11, as well as to mpMRI acquired during PET/MRI for the localization and staging of low-risk and intermediate-risk PC. New lesions identified on PET/MRI and not known from prior systematic prostate biopsy will be confirmed by targeted biopsy and GRPr and PSMA status will be evaluated with specific immunohistochemical stains [1, 2].

Aim 2: ^{68}Ga -RM2 PET/MRI and ^{68}Ga PSMA-11 PET/MRI prediction of PFS after local targeted therapy for PC. We will investigate if the combination of the GRPr-binding PET imaging agent, ^{68}Ga -RM2, and the most widely investigated (but not FDA-approved) PSMA-binding PET imaging agent, ^{68}Ga PSMA-11, together with mpMRI can predict PFS after local targeted therapy. We will determine if ^{68}Ga -RM2 PET/MRI and ^{68}Ga -PSMA-11 PET/MRI assessment at 6-months follow-up will predict PFS at 24 months based on standard clinical follow-up (PSA, imaging, tissue diagnosis).

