6.2 Imaging Days

Subjects will undergo 2 separate clinic visits not less than 3 days apart for imaging before therapy and two separate clinic visits for imaging after therapy. After the 1st scan, the 2nd scan will only occur after the follow-up with the patient for the 1st scan, and after a minimum of 3 days have elapsed. On each imaging day, subjects will receive an intravenous (IV) injection of investigational

imaging agent (⁶⁸Ga-RM2 or ⁶⁸Ga-PSMA11) and undergo PET/MRI image collection as described above.

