6.3 Follow-up

Active subject participation ends after the 24 to 72 hour Safety Follow-up after the 2nd post-therapy scan. Investigators will follow subjects by chart review for 12 months post-scan to record any standard of care biopsies or imaging results. The investigators will assist with identification of lesions that can be biopsied, based on ⁶⁸Ga-RM2 and/or ⁶⁸Ga-PSMA11 PET/MRI findings.

If a subject transfers clinical care outside of Stanford Healthcare during the chart review clinical follow-up period, investigators will request permission to contact the treating physician.

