7. STUDY CALENDAR

	Pre-Study	Scan Date	24 to 72 hours Post-Scan	12 months
Informed consent	X			
Demographics	X			
Medical history	X			
⁶⁸ Ga-RM2		X ^a		
⁶⁸ Ga-PSMA11 (\geq 3 days and \leq 2 weeks)		X ^a		
Follow-up call to participant (24 to 72 hours)			X	
Chart review ^b				X

a: Subjects will undergo either ⁶⁸Ga-RM2 PET/MRI followed within 2 weeks by ⁶⁸Ga-PSMA11 PET/MRI, or ⁶⁸Ga-PSMA11 PET/MRI followed within 2 weeks by ⁶⁸Ga-RM2 PET/MRI. After the 1st scan, the 2nd scan will only occur after the follow-up with the patient for the 1st scan, and after a minimum of 3 days have elapsed. This will be repeated approximately 6 months after HDR local treatment, prior to standard of care biopsy to evaluate for residual disease in the prostate.

b: Subjects will be followed by chart review for 24 months from initial scan date. If a subject transfers clinical care from Stanford HealthCare, investigators may request records from the treating physician.

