10.4 Accrual estimates

We expect the accrual of 20 patients each year for 5 years. This is achievable given our experience with other protocols and the support from the referring physicians, Drs [name], [name] and [name] who run the HDR Brachytherapy Clinic at the Stanford Cancer Institute.

Potential difficulties and limitations: All patients will first be seen by a Stanford Cancer Institute

[figure not shown]

Figure 11: Benign human prostate and high-grade human prostate cancer (Gleason 4+4) were stained with anti-PSMA (Santa Cruz, sc-514444, 1:100 dilution) and anti-GRPR (Abcam, #39883, 1:100 dilution) antibody. Scale bar represents 100 microns

physician and then referred if appropriate on clinical grounds for this study. SCI has a substantial volume of men with PC. We do not anticipate any difficulty in recruiting 100 men at Stanford with PC over the period of the grant since referring physicians from Radiation Oncology are supporting the study. We previously enrolled 10 patients included in a prior PET/MRI pilot study in less than 2 months.

Based on our preliminary experience in patients with PC we do not expect any technical problems. We already hold FDA-approved INDs for ^{68}Ga -RM2 PET imaging (IND # [REDACTED]) and ^{68}Ga -PSMA-11 PET imaging (IND # 128379). We have already imaged 38 PC patients at initial diagnosis

($n=9$) or BCR ($n=29$) with both ^{68}Ga -RM2 PET and ^{68}Ga -PSMA-11 PET. Therefore, we do not anticipate problems enrolling participants in this study.

Lastly, we successfully tested in-house the PSMA and GRPr IHC stains both in benign prostate tissue and PC, as shown in **Figure 11**. Therefore, we do not anticipate issues with the IHC analyses of tissue samples from the enrolled participants.

11. REFERENCES:

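### Chart review and primary completion are timed from the first scan, so no stated follow-up window reaches 24 months after local therapy, and the PFS time origin is not defined

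*Combined protocol and SAP*

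**What the plan says.** - **Objective.** Section 1 describes Aim 2 as "prediction of PFS after local targeted therapy for PC" and gives the horizon as 24 months. Section 2.5 lists prediction of PFS at 24 months within a primary objective. Section 10.2 times the second assessment (T1) at 6 months after treatment starts. No section states the date from which PFS is counted.
- **Primary completion.** Section 3.4.1: "The study will reach primary completion 24 months from the time the last subject completes the first scan".
- **Chart review.** Section 7, footnote b: "Subjects will be followed by chart review for 24 months from initial scan date". Section 6.3: "Investigators will follow subjects by chart review for 12 months post-scan to record any standard of care biopsies or imaging results". The chart-review column of the calendar is also headed 12 months.
- **Order of events.** Section 6.2: "Subjects will undergo 2 separate clinic visits not less than 3 days apart for imaging before therapy". On the post-therapy scans, footnote a of the calendar says: "This will be repeated approximately 6 months after HDR local treatment".
- **End of study.** Section 3.4.2: "The study will reach study completion 84 months from the time the study opens to accrual". Section 10.4: "We expect the accrual of 20 patients each year for 5 years". Section 10.3 gives the second primary outcome a timeframe of 84 months.

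**The concern.** The clock for observing outcomes and the natural clock for PFS start on different dates. Therapy always comes after the first scan, so a window of 24 months from that scan closes before month 24 after therapy for every man. The 12-month window closes earlier still. The trial would therefore not record what its own objective asks for, namely whether a man is progression-free 24 months after treatment. Progressions that fall between the end of the window and month 24 are lost from an analysis that expects few events: Section 10.2 assumes that 20% of responders progress by two years. The fixed end date adds a second exposure, because it leaves no room for the interval between scan and therapy or for slower accrual.

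**Working it through.** **Inputs.** 100 participants and 20 a year (Sections 2.5 and 10.4); 24 months from the first scan (3.4.1, footnote b); 12 months after a scan (6.3); post-therapy scans at about 6 months (Section 7); 20% of responders progressing by two years (10.2). The lag L from first scan to therapy is at least 3 days (0.1 month), from Section 6.2. Its full length is not stated, so I assume a range up to 3 months.

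**Step 1: reproduce month 84.** 100 / 20 × 12 = 60 months of accrual, and 60 + 24 = 84. This matches Section 3.4.2 exactly; slack is 0.

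**Step 2: follow-up after therapy under each written window.**
- Footnote b: 24 − L months, i.e. 23.9 (L = 0.1), 23.5 (0.5), 23 (1) or 21 (3).
- Section 6.3, counted from the second post-therapy scan (the scan named in its preceding sentence): about 6 to 6.5 months plus 12, i.e. 18 to 18.5 months.
- Section 6.3, counted from the first scan: 12 − L, i.e. under 12 months.

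None reaches 24.

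**Step 3: events lost.** With a constant hazard (assumption) set to 20% at 24 months, the proportion progressing by month t is 1 − 0.8^(t/24).

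| Months after therapy | Proportion progressing | Share of month-24 events lost | Events in 75–80 responders |
|---|---|---|---|
| 24 | 20.0% | 0 | 15.0–16.0 |
| 23.9 | 19.93% | 0.4% | 14.9–15.9 |
| 23.5 | 19.6% | 2% | 14.7–15.7 |
| 21 | 17.7% | 11% | 13.3–14.2 |
| 18 | 15.4% | 23% | 11.6–12.3 |

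The share lost is 1 − (proportion / 20%); for example, 1 − 17.74/20 = 11%.

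**Step 4: other time origins.** If PFS ran from the first scan, footnote b would reach month 24 exactly, with no margin. If it ran from the 6-month scan, month 24 would fall 30 + L months after the first scan, and footnote b would be short by 6 + L months.

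**Step 5: what month 84 does alone.** With even accrual, participant i has his first scan at month 0.6i and reaches 24 months after therapy at month 0.6i + L + 24. This exceeds 84 for 1, 1, 2 or 5 of 100 men at L = 0.1, 0.5, 1 or 3. The last man needs month 84.1, 84.5, 85 or 87.

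**Step 6: slower accrual (illustrative rates).** At 18 a year, accrual takes 100 / 18 × 12 = 66.7 months and primary completion falls at month 90.7. At month 84, (66.7 − 60) × 1.5 = 10 men have less than 24 months from first scan. At 15 a year, accrual takes 80 months and primary completion falls at month 104. Then 20 × 1.25 = 25 men are short, and the last is 84 − 80 = 4 months past his first scan, before his post-therapy imaging.

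**The case against.** The strongest reply is that the protocol does not say PFS is counted from therapy. Counted from the baseline scan, footnote b just reaches the horizon. That stands as far as it goes, and it is why the undefined origin is part of this point. Therapy remains the best-supported reading: the Aim 2 title refers to PFS following treatment, T1 is timed from treatment, and the 20% figure applies to treatment responders.

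The reply also limits the size. The only documented lag is 3 days, which costs about 0.4% of events. The PFS analyses in Section 10.2 are log-rank and Cox, which handle censored times. Section 10.2 also ranks the PFS comparison as a secondary hypothesis, although Section 2.5 places PFS in a primary objective.

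A reader might infer four stronger things that the documents do not support:
- **That month 84 leaves nobody observed to 24 months after therapy.** At planned accrual it cuts off only the last 1 to 5 men. The result for all men comes from the chart-review windows.
- **That PFS cannot be estimated.** Only status at month 24 after therapy goes unobserved; shorter follow-up still supports the planned tests.
- **That Sections 3.4.1 and 3.4.2 contradict each other.** At 20 a year both give month 84. They conflict only if accrual is slower, and the protocol expects no recruitment difficulty.
- **That about a quarter of events are lost under footnote b because progression is found at six-monthly visits.** No such schedule appears; follow-up is review of routine records.

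**Conclusion.** The point holds in this form. Counted from therapy, no written chart-review window reaches 24 months for any man. Under footnote b the shortfall is 3 days to about 3 months, or about 0.4% to 11% of month-24 events. That range rests on an assumed lag of up to 3 months and a constant hazard. Under Section 6.3 the shortfall is about 6 months or more, so the 12-month statements are the larger part of the gap. Correcting 12 to 24 months alone would still leave the clock starting at the wrong event. The absence of slack at month 84 is a lesser matter at planned accrual, but any rate below 20 a year would put study completion before primary completion. The change is worth making because it is cheap and the horizon belongs to a primary objective.

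**What to change.** 1. Define the PFS time origin as the start of local therapy.
2. In Section 6.3, footnote b and the calendar column, run chart review to at least 24 months from that date, and include the first standard-of-care record at or after month 24 so that status at the horizon is documented. All three places must change; if Section 6.3 stays as it is, follow-up still ends about 18 months after therapy or earlier.
3. In Section 3.4.1, time primary completion from the same origin.
4. In Section 3.4.2, and in the 84-month timeframe in Section 10.3, replace the fixed month with the date the last participant reaches that point.

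The cost is protocol wording, some extra chart review per man, and a study end slightly later than month 84: about 84.1 to 87 at planned accrual for a lag of 3 days to 3 months, plus any wait for the first record at or after month 24.

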4. IMAGING AGENT INFORMATION

4.1 Study Agents $^{68}\text{Ga-PSMA-11}$ and $^{68}\text{Ga-RM2}$

$^{68}\text{Ga-PSMA-11}$

This study will use $^{68}\text{Ga-PSMA-11}$ as the PET radiopharmaceutical. This agent has previously been identified as DFKZ-11; HBED-CC PSMA; or the “Heidelberg compound.”

The administered dosage of $^{68}\text{Ga-PSMA-11}$ is 111 to 259 mBq (3 to 7 mCi) IV. We will use $^{68}\text{Ga-PSMA-11}$ as the PET radiopharmaceutical. There are 2 publications on dosimetry for $^{68}\text{Ga-PSMA-11}$ (PMID: 27260521; 28012435). The first lists 0.0236 mSv/MBq for the mean effective dose, while the other indicates 0.0258 mSv/MBq. We used the maximum potential administered

activity of 7 mCi and the higher of the reported dosimetry values. Therefore, $259 \text{ mBq} \times 0.0258 \text{ mSv/MBq} = 6.68 \text{ mSv}$.

To summarize the results of the published human studies, there were no observed adverse events to the radiopharmaceutical. The measured dosimetry showed that the critical organ with ^{68}Ga -PSMA-11 is the spleen, followed by the stomach wall; pancreas; and bladder wall. The effective dose of ^{68}Ga -PSMA-11 reported (0.0258 mSv/MBq) is similar to those of ^{68}Ga -DOTA-TOC (0.023 mSv/MBq), ^{68}Ga -DOTA-NOC (0.025 mSv/MBq), ^{68}Ga -DOTA-TATE (0.021 mSv/MBq) and ^{68}Ga -NOTA-RGD (0.022 mSv/MBq) [85-88].

^{68}Ga -RM2

This study will also use ^{68}Ga -RM2 as the PET radiopharmaceutical. The administered dosage is $140 \pm 20\%$ mBq IV. Measured human dosimetry data are available from published data [89].

^{68}Ga -RM2 is rapidly excreted through the kidneys to the urinary bladder and accumulated predominantly in the pancreas and liver. Maximum peak uptake of the total injected radioactivity was seen in the urinary bladder contents and the liver, with approximately 36% and 14%, respectively.

The organ with the highest absorbed dose was the urinary bladder wall at 0.61 mSv/MBq, followed by the pancreas at 0.51 mSv/MBq. The mean effective dose (14) was 0.051 mSv/MBq. Thus, the effective dose from a 140 MBq injected radioactivity is 7.7 mSv, which could be reduced to roughly 4.76 mSv with frequent bladder voiding (1-h voids).

To summarize the results of the published human dosimetry study, there were no observed adverse events to the radiopharmaceutical. The measured dosimetry showed that the critical organ with ^{68}Ga -RM2 is the urinary bladder, followed by the pancreas. The effective dose of ^{68}Ga -RM2 reported (0.051 mSv/MBq) is approximately twice as much as those of ^{68}Ga -DOTA-TOC (0.023 mSv/MBq), ^{68}Ga -DOTA-NOC (0.025 mSv/MBq), ^{68}Ga -DOTA-TATE (0.021 mSv/MBq) and ^{68}Ga -NOTA-RGD (0.022 mSv/MBq) [85-88].

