2.5 Study Design

This is a NCI-funded phase II study with a total of 100 participants with known prostate cancer, scheduled to undergo HDR local therapy. All patients will first be seen by a Stanford Cancer

Institute physician and then referred if appropriate on clinical grounds to Dr [name] or his colleagues for this study. Eligible participants will undergo baseline assessments at enrollment. The following steps will take place after the participant has signed the written consent (participants will be randomized to have ^{68}Ga -RM2 first followed by ^{68}Ga -PSMA11 within 2 weeks or ^{68}Ga -PSMA11 first followed by ^{68}Ga -RM2 within 2 weeks [50/50 chance for each schedule]). After the 1st scan, the 2nd scan will only occur after the follow-up with the patient for the 1st scan, and after a minimum of 3 days have elapsed.

Scan 1

1. Participants will be given a copy of the consent form s/he signed
2. Participant will be asked to drink 1 to 2 glasses of water before arrival at the clinic
3. Vital signs (heart rate, blood pressure) will be recorded
4. Participant will be injected IV with $140 \pm 20\%$ mBq of ^{68}Ga -RM2 **OR** 3 to 7 mCi of ^{68}Ga -PSMA11.
5. Participant will void immediately prior to the scan
6. Approximately 45 minutes after the radiopharmaceutical IV administration, data acquisition will begin in the pelvic region and move toward the head. First, localizer MRI scans will be performed to define the table positions. After correct positioning of the spatial acquisition windows is ensured, the combined PET/MRI acquisition will be initiated with 3 to 5 table positions at a 2 to 4-min acquisition time per table position.
7. Participants will be dismissed.
8. Vital signs (heart rate, blood pressure) will be recorded again at the completion of the study
9. Participants will be contacted at 24 to 72 hours following the scan in order to capture potential occurring Adverse Events.

Scan 2

1. Participant will be asked to drink 1 to 2 glasses of water before arrival at the clinic
2. Vital signs (heart rate, blood pressure) will be recorded
3. Participant will be injected IV with 3 to 7 mCi of ^{68}Ga -PSMA11 **OR** $140 \pm 20\%$ mBq of ^{68}Ga -RM2 (ie, the radiopharmaceutical not administered for Scan 1)
4. Participant will void immediately prior to the scan

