8. ADVERSE EVENTS AND REPORTING PROCEDURES

8.1 Potential Adverse Events

The administration of the radioactive substance will feel like a slight pinprick when given by IV injection. Patients who are claustrophobic may feel some anxiety while positioned in the scanner. Also, some patients find it uncomfortable to hold one position for more than a few minutes. The subjects will not feel anything related to the radioactivity of the substance in their body. Because the radioactivity is very short-lived, the radiation exposure is low. The substance amount is so small that it does not affect the normal processes of the body.

This research study involves exposure to radiation from two (before and after treatment) ^{68}Ga -PSMA-11 PET/MRI. There is no radiation exposure from MRI. The effective dose from one typical maximum of 259 mBq (range: 3 to 7 mCi) administration of ^{68}Ga -PSMA-11 is 6.68 mSv. Therefore, the effective dose from two ^{68}Ga -PSMA-11 PET/MRI is 13.36 mSv, approximately equal to 26% of the limit that radiation workers (eg, a hospital X-ray technician) are allowed to receive in one year.

This research study also involves exposure to radiation from two (before and after treatment) ^{68}Ga -RM2 PET/MRI. There is no radiation exposure from MRI. The amount of radiation from one administration of 140 mBq of ^{68}Ga -RM2 is 4.76 mSv. Therefore, the effective dose from two ^{68}Ga -RM2 PET/MRI is 9.52 mSv, approximately equal to 20% of the limit that radiation workers (for example, a hospital X-ray technician) are allowed to receive in one year.

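### Section 8.1 states the 68Ga-RM2 dose at nominal activity and without the hourly voiding it depends on; separately, the 7.7 mSv in section 4.1 is not 0.051 × 140

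*Combined protocol and SAP*

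**What the plan says.** All references are to the combined protocol and SAP. It writes mBq in several places; I read this as MBq throughout.

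- **Section 4.1, RM2 coefficient.** "The mean effective dose (14) was 0.051 mSv/MBq". Later in the same section the RM2 effective dose "reported (0.051 mSv/MBq) is approximately twice as much as those of" four other gallium-68 tracers, so the coefficient is stated twice.
- **Section 4.1, RM2 dose.** As a consequence of that coefficient, the section states: "dose from a 140 MBq injected radioactivity is 7.7 mSv, which could be reduced to roughly 4.76 mSv with frequent bladder voiding (1-h voids"). The permitted activity is 140 MBq plus or minus 20%.
- **Section 8.1, RM2 dose.** "The amount of radiation from one administration of 140 mBq of ^{68}Ga -RM2 is 4.76 mSv". The dose from two 68Ga-RM2 "PET/MRI is 9.52 mSv, approximately equal to 20% of the limit that radiation workers" may receive in a year. Neither voiding nor the 20% tolerance is mentioned.
- **Sections 4.1 and 8.1, PSMA-11 dose.** "The effective dose from one typical maximum of 259 mBq (range: 3 to 7 mCi) administration of" 68Ga-PSMA-11 is 6.68 mSv. Section 4.1 explains that this takes the top of the activity range and the larger of two published coefficients.
- **Section 2.5, procedures.** For each scan the instruction is "Participant will void immediately prior to the scan". Acquisition starts about 45 minutes after injection (45 to 60 minutes for Scan 2). No later void is scheduled; after acquisition the Scan 1 list says "Participants will be dismissed". Section 5.2 adds no voiding instruction.

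**The concern.** There are two separate points.

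The first is the more important. In section 4.1, 4.76 mSv is what the dose could come down to under a particular voiding regimen. In section 8.1 the same number appears as the dose, with the regimen gone, and the scan procedures do not ask for that regimen. Voiding matters for this tracer: section 4.1 names the bladder as the critical organ and puts peak bladder content at about 36% of the injected activity. The two tracers are also put on different footings: PSMA-11 at its highest permitted activity and higher coefficient, RM2 at its nominal activity and lower, voiding-reduced dose. A reader comparing 4.76 with 6.68 mSv would conclude that RM2 is the lower-dose scan. Without the voiding reduction the order reverses.

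The second is a product in section 4.1 that does not equal its factors.

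What is at stake is the accuracy of the exposure described to the IRB and in anything drawn from section 8.1. Each participant is to have two RM2 scans.

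**Working it through.** **Formula.** Effective dose (mSv) = activity (MBq) × coefficient (mSv/MBq).

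**Figures that reproduce**
- PSMA-11, one scan: 259 × 0.0258 = 6.68 mSv. Two scans: 2 × 6.68 = 13.36 mSv.
- RM2, two scans as stated: 2 × 4.76 = 9.52 mSv.

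**Figure that does not reproduce**
- RM2 in section 4.1: 0.051 × 140 = 7.14 mSv, against 7.7 stated. The gap is 0.56 mSv (0.56 / 7.14 = 7.8%).
- Rounding of the coefficient does not explain it: 0.0505 × 140 = 7.07 and 0.0515 × 140 = 7.21.
- 7.7 mSv at 140 MBq needs 7.7 / 140 = 0.055 mSv/MBq. At 0.051 it needs 7.7 / 0.051 = 151 MBq.

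**Inputs for the range**
- Maximum RM2 activity: 140 × 1.2 = 168 MBq.
- Coefficient implied by the hourly-voiding dose: 4.76 / 140 = 0.034 mSv/MBq.
- Coefficient without that reduction: 0.051 mSv/MBq (section 4.1).
- Annual worker limit: not given. The percentages in section 8.1 imply 9.52 / 0.20 = 47.6 and 13.36 / 0.26 = 51.4 mSv. I assume 50 mSv.

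| RM2 basis | One scan (mSv) | Two scans (mSv) | Ratio to 9.52 | Share of 50 mSv | All four scans, adding 13.36 (mSv) |
|---|---|---|---|---|---|
| 140 MBq, 0.034 (as in 8.1) | 4.76 | 9.52 | 1.0 | 19% (stated as 20%) | 22.88 |
| 168 MBq, 0.034 | 5.71 | 11.42 | 1.2 | 23% | 24.78 |
| 140 MBq, 0.051 | 7.14 | 14.28 | 1.5 | 29% | 27.64 |
| 168 MBq, 0.051 | 8.57 | 17.14 | 1.8 | 34% | 30.50 |

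If 0.055 turned out to be the right coefficient, the last row would be 168 × 0.055 = 9.24 mSv per scan and 18.48 mSv for two.

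**Comparison between tracers.** As stated, RM2 is below PSMA-11 (4.76 against 6.68 mSv per scan). Without the voiding reduction it is above it at nominal activity (7.14) and at maximum activity (8.57).

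**The case against.** The case on the other side has five parts.

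- **The procedures are not a no-voiding scenario.** Participants drink one or two glasses of water before arrival, void within about the first hour after injection, and are free to void on leaving. This stands in part: 14.28 and 17.14 mSv are upper bounds, not corrected values. But one void is not an hourly regimen, so it does not establish 4.76 mSv either.
- **Stating the condition, or giving both values as section 4.1 does, would be enough.** Giving both would cure the omission. Attaching the condition alone would describe a dose under a regimen that nobody is told to follow. Neither addresses the activity tolerance.
- **Section 8.1 labels the activity behind each figure.** It does, and 140 MBq is the middle of a symmetric range, so the activity used is not misstated. The two tracers are still presented side by side on different bases, and the more favourable basis is given to RM2.
- **7.7 mSv may belong to another activity.** 0.051 × 150 = 7.65, which rounds to 7.7. That may be how the figure arose, and the documents cannot settle it. It does not rescue the sentence, which assigns 7.7 mSv to 140 MBq, the activity used throughout the plan.
- **The 7.7 slip is small and errs upwards.** Agreed. It overstates the dose by 0.56 mSv and is not carried into section 8.1.

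**Conclusion.** Both points hold.

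Section 8.1 presents a conditional dose at nominal activity as the exposure. For two RM2 scans it states 9.52 mSv, where the plan's own figures give 9.52 to 17.14 mSv between nominal and maximum activity, depending on voiding. The documents do not say which coefficient fits a single void about 45 minutes after injection, so the position within that range is unknown. Over all four scans the stated components sum to 22.88 mSv, with an upper bound of 30.50 mSv.

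In section 4.1, 7.7 mSv does not follow from 0.051 mSv/MBq at 140 MBq; the product is 7.14 mSv.

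These conclusions take 0.051 as correct. The 0.034 is back-calculated from a dose that section 4.1 itself calls approximate, and the percentages assume a 50 mSv limit. The consent form and some pages of the protocol were not in the text I checked, so I make no claim about what they say on voiding or dose. This is a matter of risk disclosure; it does not touch the sample size or the analysis. It should be corrected.

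**What to change.** **Section 4.1.** Check the dosimetry source. If 0.051 is right, replace 7.7 mSv with 7.14 mSv. If the source supports 7.7 mSv at 140 MBq, change the coefficient to 0.055 in both places where it appears.

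**Section 8.1.** Take one of two routes:

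1. Report RM2 on the same basis as PSMA-11, as a maximum: 168 MBq without the voiding reduction, giving 8.57 mSv per scan and 17.14 mSv for two (9.24 and 18.48 if 0.055 is confirmed).
2. Keep the voiding-reduced basis at maximum activity (5.71 mSv per scan, 11.42 for two), but only if section 2.5 instructs hourly voiding after RM2 injection and section 8.1 states that condition.

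In either case, restate the share of the worker limit (34% or 23% at an assumed 50 mSv), give the limit used, and update any participant text that draws on section 8.1.

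**Cost.** Wording in sections 4.1 and 8.1 and in text derived from them, and a less favourable stated exposure. The second route adds one voiding instruction for the RM2 scans before and after treatment. The design does not change.
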